4.1 Enrollment/Baseline Visit

Prior to enrollment in the clinical investigation, site personnel will screen potential candidates by reviewing the patient medical records against the inclusion and exclusion criteria. It is expected that the medical records will contain adequate and accurate information to determine if the patient meets these criteria. A Screening CRF will be completed for every patient who signs a consent form.

If a patient meets all inclusion criteria and does not meet any of the exclusion criteria, the patient shall be eligible for the investigation.

The study site personnel will follow the informed consent process set forth in Section 5.6. If the patient agrees to participate, the site will obtain the signature and date from the patient on the approved Patient Informed Consent (PIC) form (previously approved by Ethics Committee and the Sponsor). If the patient does not sign and date the Patient Informed Consent (PIC), they cannot participate in the investigation and no further CIP required activities are allowed.

A patient becomes a subject once he/she has been fully informed about the investigation, has agreed to participate, signs and dates the PIC and therefore is enrolled in the investigation.

NOTE: As soon as the subject signs the Patient Informed Consent, adverse events need to be reported according to the guidelines mentioned in Section 5.6.

The EC should be notified appropriately about any CIP deviations with regards to obtaining informed consent.

If new information becomes available during the clinical study that can significantly affect a patient's future health and medical care, that information will be provided to the patient(s) in written form.

The following information will be collected at the baseline visit either from hospital records or through patient interaction documented in the hospital records. All baseline activities will be performed after the patient is enrolled in the investigation. Tests and procedures required at baseline will be completed within 90 days after enrollment and must be completed prior to

procedure. The ablation procedure must be performed within 30 days of the baseline tests and procedures.

4.1.1 Medical History

A complete medical history of the subject will be reviewed and recorded including:

- Hypertension, renal disease, cardiovascular disease, neurological disease, obstructive sleep apnea, hyperlipidemia, diabetes (Type I and II), smoking, thyroid disease, liver disease, chronic obstructive pulmonary disease, and alcohol consumption
- A description of the subject's anti-hypertensive and anti-arrhythmic drug regimen.
- A description of the subject's arrhythmia history.

4.1.2 12-Lead ECG

The subject will undergo a 12-Lead ECG assessment.

4.1.3 Physical Assessment

The subject will have a physical assessment recording at the baseline visit to capture the following:

- Age
- Gender
- Height (only at baseline)
- Weight

4.1.4 Office Blood Pressure

Office Blood Pressure measurements will be recorded as the average Blood Pressure of three measurements. If there is a change in medication after the office Blood Pressure assessment is completed an additional set of office Blood Pressure measurements is required to determine eligibility.

Measurements should be taken according to Standard Joint National Committee VII Guidelines / ESC and ESH Guidelines^{26,27}, refer to Appendix A for Office Blood Pressure instructions.

4.1.5 Ambulatory Blood Pressure

To ensure proper patient selection for inclusion in the study subjects must have a daytime mean Ambulatory Blood Pressure (ABP) measurement of > 135 mmHg within 90 days prior to procedure.

If there is a change in medication after ABP assessment an additional ABP assessment is required to determine eligibility. In addition to the daytime mean ABP, the night time mean, and 24 hour average ABP value will be collected. When using ABP ensure that at least two measurements per hour are taken during the person's usual waking hours (for example, between 08:00 and 22:00) and 1 measurement per hour are taken during the person's usual night time hours. The average value of at least 14 measurements taken during the person's usual waking hours should be used for calculation of mean daytime value.

Measurements should be taken according to Standard Joint National Committee VII Guidelines ESC and ESH Guidelines^{26,27} refer to Appendix B for 24 Hour Ambulatory Blood Pressure instructions.

4.1.6 Blood and Urine Analysis

Blood and urine samples will be collected and analyzed as listed below.

- Serum Creatinine
- Estimated GFR (eGFR)
- Hemoglobin A1c
- Fasting glucose
- Fasting insulin
- Urine albumin-creatinine ratio
- Pregnancy test (only at baseline)

A true numeric value for the estimated GFR must be provided. If your local laboratory does not report the eGFR value beyond 60 mL/min/1.73 m² the center should use a sponsor-approved calculation tool to generate the value. The sponsor will provide an approved website(s) for this calculation to study centers.

4.1.7 Transthoracic-echocardiogram (TTE)

Transthoracic-echocardiogram (TTE) examinations will be conducted. Each site is responsible for performing the echocardiogram per their standard of care echo protocol.

4.1.8 NYHA Assessment

NYHA Assessment²⁸ will be evaluated at baseline and should be classified based on the definitions in Appendix C.

4.1.9 Quality of Life Questionnaire

EQ-5D 5L and the AFEQT questionnaires will be completed at baseline.

4.1.10 Baseline Renal Artery Anatomy Evaluation

Adequate renal artery imaging is required to occur within 90 days prior to enrollment. Computed Tomography (CT) or Magnetic Resonance (MR) angiogram are recommended, non-contrast Magnetic Resonance Imaging (MRI) and doppler evaluation or ultrasound are acceptable. It is recommended that an MRI is performed to evaluate the renal artery anatomy to reduce the risk of radiation exposure.

Renal artery evaluation data collected will include but are not limited to:

- Type of evaluation computed axial tomography (CT scan), duplex ultrasonography, angiography, Doppler, magnetic resonance (MR) angiography, or non-contrast MRI
- Length of artery(s)
- Diameter of artery(s)
- Number of main renal arteries
- Number of accessory renal arteries
- Presence and percent of stenosis
- Other abnormalities

4.1.11 Medication

The subject's baseline medication regimen, including medication name, dose, and frequency will be reviewed and recorded, making note of those medications taken specific to the subject's cardiovascular therapy. If there is a change in medication after the baseline office Blood Pressure assessment is completed, the patient should be on the new regimen for 4 weeks after which time an additional set of office Blood Pressure measurements is required to determine eligibility.

The investigator will assess that the subject was on a stable anti-hypertensive medication regimen for a period of at least 4 weeks prior to renal denervation procedure. It is recommended that the subjects maintain their enrollment anti-hypertensive regimen for a minimum of 180 days post procedure unless deemed clinically necessary. Investigators will urge subject compliance to prescribed medical regimen throughout the trial. If the subject is non-compliant without medical rationale, the subject may be discontinued from the study.

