4.11 Clinical Investigation Termination

Each subject will be followed for 2 years post ablation procedure or until time of death, loss to follow up, withdrawal or clinical investigation termination. The clinical investigation will be complete after all follow-up visits are performed, all data is received by the Sponsor and the database is locked. The study will be closed when a final report is written on the conclusions and analysis of the data.

Participation in this clinical investigation is voluntary. Subjects are free to withdraw from the clinical investigation at any time without reason. However, subjects should be strongly encouraged to complete the protocol required follow up. Should a subject wish to withdraw prior to completing 60-month follow-up, the investigator should request the subject to come in for a final visit and a Termination CRF should be completed by the site and provided to the Sponsor.

At this visit the subject should undergo the following evaluations:

• Office Blood Pressure measurement

- Blood/Urine labs
- 12 Lead ECG

In a situation where a clinical investigation withdrawal is due to an adverse event the subject should be followed until resolution of that adverse event or determination that the subject's condition is stable. Upon withdrawal from the study, data will cease to be collected on Case Report Forms.

Subjects must be informed about their right to withdraw from the investigation at any time and for any reason without sanction, penalty or loss of benefits to which the subject is otherwise entitled and withdrawal from the investigation will not jeopardize their future medical care or relationship with the investigator. Subjects will be asked to specify the reason for the withdrawal, but have the right not to answer.

The investigator may decide to withdraw a subject from the investigation at any time. The subject's future care will not be influenced by a decision, voluntary or otherwise, to withdraw from the investigation. All reasonable efforts should be made to retain the subject in the clinical investigation until completion of the investigation.

Reasons for termination include, but are not limited to, the following:

- Subject did not meet the inclusion/exclusion criteria
- Subject requests to be withdrawn from the study
- Investigator withdraws subject from the study
- Subject lost to follow-up, defined as the following: a subject will be considered

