 follow-up" after a minimum of 2 documented phone calls of a physician or delegate at the
 study site to the subject or emergency contact and a certified letter sent to the last known
 address
 - Subject death (in case of subject death, cause must be documented)
 - Subject non-compliance
- Study terminated at the local, national, or international level, at the request of Ethics Committees, regulatory authorities, or SJM.
- Subject completed study

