#### 2.4 Primary objective

The primary objective is to assess the feasibility of concomitant cardiac ablation for the treatment of atrial fibrillation and renal denervation ablation using the EnligHTN renal denervation system in achieving freedom from atrial fibrillation in patients with hypertension.

Project Code: SJM-CIP-0009 Project Name: RD+AF

The freedom from atrial fibrillation will be assessed based on electrocardiographic data during nine months following the blanking period including the one week recording coinciding with the 12 month follow-up visit (9 months following the 3 month blanking period). AF recurrence during the blanking period will not qualify as an endpoint event per protocol. Subjects may be re-treated with up to two repeat ablation procedures during the course of the study with a 3 month blanking period following the treatment. Assessment of the AF recurrence will be determined through evaluation of 12 lead ECG recordings, holter monitoring or event recorder results. AF Recurrence is defined as episodes lasting longer than 30 seconds in duration unless detected via 12-lead EKG. To count as a study-related recurrence, the AF episode must be documented on the AF Recurrence Evaluation CRF. For this study, AF also includes (documented >30 seconds) atrial flutter and atrial tachycardia.

No formal hypothesis testing will be performed. An overall percentage of subjects experiencing an event will be summarized for each randomization arm and is defined as:

Number of subjects with AF recurrence within 12 months post procedure Number of subjects with at least 12 months of follow – up or experienced AF recurrence \* 100

Subjects who exit the study prior to 12 month visit without AF recurrence will be excluded from the percentage to prevent under-estimation of the event rate. Kaplan-Meier analysis may be performed to provide freedom from atrial fibrillation rates at one year for each randomization arm using date of ablation procedure to date of first event.

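### Ending a subject's follow-up for non-compliance, combined with the SAP's primary denominator, creates avoidable selection after randomisation

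*Protocol*

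**What the plan says.** Four provisions act together.

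- **Exit.** Protocol 4.1.11, on the medication regimen: "If the subject is non-compliant without medical rationale, the subject may be discontinued from the study". The section sits under the baseline visit, but the sentence before it reads "Investigators will urge subject compliance to prescribed medical regimen throughout the trial", so the provision reaches past randomisation. Non-compliance is not defined, and no threshold or independent review is given.
- **Termination reason.** Protocol 4.11 lists "Subject non-compliance", without limiting it to medication. The same section also lets the investigator withdraw a subject at any time and lists that as a separate reason.
- **End of data.** Protocol 4.11: "Upon withdrawal from the study, data will cease to be collected on Case Report Forms".
- **Primary percentage.** SAP 2.4 divides the subjects with recurrence by "Number of subjects with at least 12 months of follow – up or experienced AF recurrence". It adds: "Subjects who exit the study prior to 12 month visit without AF recurrence will be excluded from the percentage". The stated purpose is to avoid understating the event rate.

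SAP 2.4 offers one alternative that would retain early leavers as censored, but only as an option: "Kaplan-Meier analysis may be performed to provide freedom from atrial fibrillation rates at one year for each randomization arm".

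**The concern.** The randomised difference between the arms, renal denervation, is delivered at the index procedure. A subject who later stops taking tablets can still be observed for AF, blood pressure and safety, and the visits are already scheduled. Ending observation for that reason serves no purpose that the documents state.

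The denominator makes the loss matter. Two subjects discontinued on the same day for the same reason are treated differently according to outcome: the one who has recurred stays in the primary percentage and the one who has not is removed. The exit is discretionary. Protocol 4.3 compares ablation plus denervation with ablation alone, no sham or masking is described, and renal imaging is done only in the denervation arm (Protocol 4.10.9), so the decision is presumably taken with knowledge of the allocation. Medication-taking also comes after randomisation and may itself differ by arm, for example if denervation lowers blood pressure, so unequal exit does not require bad faith.

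At stake are the per-arm recurrence percentages, which are the trial's main result, and the blood-pressure and safety observations that would have followed the exit.

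**Working it through.** The plan states no exit rate, expected recurrence rate or power, so there is no planned figure to reproduce. What can be checked is how the SAP 2.4 formula behaves.

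**Inputs.** SAP 2.2 gives 75 patients with at least 50 in the denervation arm; 75 × 2/3 = 50, leaving 25 controls. Protocol 7.2 gives about 100 patients, which at 2:1 would be about 67 and 33; the smaller SAP figure is used here. All recurrence rates and exit fractions below are assumptions.

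**Case 1: exit unrelated to outcome.** Let *p* be the true 12-month recurrence, *q* = 1 − *p*, and *d* the fraction who exit. Assume exit times uniform over months 0–12, no countable events in the 3-month blanking period, and a constant hazard over months 3–12.

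- Probability that a leaver has recurred before exit: *E* = (9/12) × [1 − (*q* − 1)/ln *q*].
- Expected SAP percentage: [(1 − *d*)*p* + *dE*] / [(1 − *d*) + *dE*].

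For *p* = 0.40: *E* = 0.75 × (1 − 0.7830) = 0.1627. With *d* = 0.10 the result is (0.36 + 0.0163)/(0.90 + 0.0163) = 0.3763/0.9163 = 41.1%.

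| True rate | 10% exit | 20% exit |
|---|---|---|
| 30% | 30.9% | 32.0% |
| 40% | 41.1% | 42.3% |
| 50% | 51.1% | 52.5% |

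If the true rates are equal and only one arm has exits, the spurious difference is 0.9 to 1.1 points at 10% exit and 2.0 to 2.5 points at 20%, against the arm with the exits. With equal exit in both arms the difference is zero, although both rates are inflated.

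The SAP's stated purpose can be tested in the same way. Keeping leavers in the denominator as recurrence-free gives 0.3763/1 = 37.6% for a true 40%, which is too low. Dropping them gives 41.1%, which is too high. Censoring them at exit is the approach that is consistent here.

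**Case 2: exit related to outcome.** Assume 40% recurrence under full follow-up and that every subject removed would have stayed recurrence-free.

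- Control: 10/25 = 40.0%. With 1 removed, 10/24 = 41.7%; with 3, 10/22 = 45.5%; with 5, 10/20 = 50.0%.
- Denervation: 20/50 = 40.0%. With 1 removed, 20/49 = 40.8%; with 5, 20/45 = 44.4%.

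Removing 3 to 5 controls and no denervation subjects gives an apparent difference of 5.5 to 10 points. This requires 12% to 20% of controls (3/25 to 5/25), or 20% to 33% of the 15 recurrence-free controls, to leave.

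**Case 3: direction.** Suppose 20 recurrences are observed in the denervation arm and 5 recurrence-free subjects leave. The SAP reports 20/45 = 44.4%. Full follow-up would give between 20/50 = 40.0% (none would have recurred) and 25/50 = 50.0% (all would have). The reported figure can therefore be too high or too low.

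**The case against.** Several points on the other side stand.

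- A reader might infer that the primary percentage is always biased upward. The documents do not support that. Protocol section 2 says that elevated blood pressure can play a major role in developing and maintaining AF, so subjects off their antihypertensive drugs may be at higher risk. Dropping them would then understate the rate, as Case 3 shows.
- A reader might infer that the rule favours denervation, or take 5.5 to 10 points as the expected error. It applies to both arms, and nothing in the documents suggests exits that are so frequent or so one-sided.
- Only exits before the 12-month visit without recurrence touch the primary percentage. The trial is descriptive (SAP 2.2), so reported rates are affected, not a type I error.
- There is mitigation. The exit is permissive, and Protocol 4.11 asks for reasonable efforts to retain subjects. A subject who wishes to withdraw is asked to a final visit with office blood pressure, laboratory tests and a 12-lead ECG. Unresolved adverse events are followed to resolution (Protocol 5.7.8). SAP 2.2 uses all available data from withdrawn subjects where applicable, so data from before the exit are kept.
- Deleting the medication sentence alone would not close the route, because general investigator withdrawal would remain, as would the denominator rule for every other early exit.

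The mitigation does not remove the problem. The specific exclusion in SAP 2.4 still governs the primary percentage, the final visit includes no 7-day recording, and Kaplan-Meier remains optional.

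**Conclusion.** The concern holds, with limits. The two documents together allow an investigator who presumably knows the allocation to end observation for non-compliance, and then condition the primary denominator on whether recurrence had already been seen. This is avoidable selection after randomisation.

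Inflation within an arm follows if exits are non-informative or would have stayed recurrence-free; the rate can be too low if the leavers would have recurred. A bias between arms needs differential exit, which is possible but not shown. Under the Case 1 assumptions the spurious difference is about 1 to 2.5 points for 10% to 20% exit in one arm only. The 5.5 to 10 points are a worst case. Each removal shifts the control arm about twice as much as the denervation arm (1.7 against 0.8 points in Case 2).

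That allocation is known is an inference from the absence of any described masking or sham; the documents do not use the term open-label. Blood-pressure and safety follow-up is lost only for the period after exit.

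**What to change.** 1. In Protocol 4.1.11 and 4.11, state that non-compliance is recorded as a deviation and is not a reason to end follow-up. The subject stays in the planned AF, blood-pressure and safety follow-up to 24 months unless consent is withdrawn, and all these data are analysed.
2. Apply the same rule to the general investigator-withdrawal route in Protocol 4.11, so that investigator discretion does not end observation.
3. In SAP 2.4, make the Kaplan-Meier analysis required instead of optional, with the remaining early exits censored at exit. This assumes that those exits are unrelated to prognosis; reporting them by arm and reason would let a reader form the bounds in Case 3.

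The change concerns observation only and leaves the medication regimen as it is. It adds no visits. It costs a protocol amendment, with ethics committee notification or approval and renewed consent where Protocol section 10 requires them. Some blood-pressure values will come from subjects off their regimen; these can be flagged.

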4.1.12 Adverse Events

Report any adverse events or adverse device effects since consent and document in source documents. Report the adverse event according to specifications in Section 5.7.

4.2 Pre-Cardiac Ablation Procedure

Patients shall undergo pre-ablation tests as per the hospital standard of care to ensure

SJM CONFIDENTIAL AND PROPRIETARY

 \odot 2013 – St. Jude Medical Cardiovascular Division: All rights reserved. No portion of this work may be reproduced in whole or in part without the express written permission of St. Jude Medical Cardiovascular Division.

Clinical Investigational Plan: RDN + AF

they can suitably undergo RF catheter ablation therapy for the treatment of paroxysmal or persistent atrial fibrillation.

4.3 Randomization Procedure

Using a 2:1 randomization scheme, each subject will be randomized to an atrial ablation procedure with concomitant renal denervation or an atrial ablation procedure alone.

Each subject will be randomized after the following is completed:

- Baseline evaluation
- Inclusion/Exclusion evaluation
- Subject signs study-specific consent form
- Cardiac ablation procedure for treatment of atrial fibrillation is complete.

4.4 Cardiac Ablation Procedure

Patients will undergo atrial ablation with the Safire Blu Duo, Therapy™ Cool Path Duo or Therapy Cool Flex Ablation Catheter in conjunction a steerable introducer (Agilis NxT) and with the use of the EnSite Velocity System. Any additional navigation and visualization tools or diagnostic catheters may be used at the discretion of the catheter operator and per the center's standard of care.

The ablation strategy utilized for treatment of paroxysmal or persistent atrial fibrillation will follow the center's standard of care and will be recorded on the Procedure Case Report Form.

All cardiac related adverse events occurring during the cardiac ablation procedure will be collected.

4.4.1 Concomitant Cardiac Procedures

Creation of cavo-tricuspid isthmus lesion set for the creation of bi-directional block will be allowed, if the subject has a documented history of typical AFL or if typical AFL is induced during the procedure.

4.4.2 End of Cardiac Ablation

Pacing techniques may be used for determination of electrical isolation of targeted pulmonary veins, bi-directional block along cavo-triscuspid isthmus etc. as applicable. Electrograms (EGM) will be recorded in the source documentation as representation of the techniques used and to ascertain this determination.

The total RF duration, cardiac ablation duration and fluoroscopy times and dosage will be recorded.

